RTA 408 is readily absorbed and distributed into ocular tissues after topical ocular administration, with sustained concentrations observed for at least 24 hours after the last dose. This ocular pharmacokinetic profile is consistent with the efficacy observed with twice daily ocular dosing in rabbits.

Ocular GLP toxicity studies have been completed with RTA 408 Ophthalmic Suspension in rabbits and monkeys with repeated (4x/day) administration of RTA 408 (0.1%, 0.3%, and 1%) for 28 days. As expected, systemic exposure to RTA 408 was very low in rabbits and monkeys, with maximum concentrations (C_{max}) on Day 28 of approximately 3.0 and 2.6 ng/mL, respectively. Overall, the topical ocular administration of RTA 408 Ophthalmic Suspension, at concentrations of 0.1%, 0.3%, and 1% four times daily for 28 days in rabbits, but not monkeys, produced ocular irritation, but did not cause any ocular or systemic toxicity in rabbits or monkeys. Thus, the no-observed-adverse-effectlevel (NOAEL) was determined to be at least 1% RTA 408 Ophthalmic Suspension administered 4x/day for 28 days in rabbits and monkeys. The conjunctival irritation observed in the rabbit ocular GLP toxicity study was reversible, was not observed in a non-GLP study in rabbits, was not observed in the monkey ocular GLP toxicity study, and is readily monitorable in the clinic.

Although it is highly unlikely that meaningful systemic exposure will result following topical ocular administration in humans, the systemic toxicity potential of RTA 408 has been extensively investigated in rats and monkeys, with daily oral administration for up to 6 months in rats and 9 months in monkeys.

Based on an integrated assessment of the nonclinical data, it is concluded that RTA 408 has an acceptable safety profile for topical ophthalmic use as indicated in the proposed topical ocular study in patients following uncomplicated cataract surgery at concentrations of 0.5% and 1.0% with a BID dosage regimen.

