6.2 Safety Measures

- Slit lamp biomicroscopy
- Pin-hole visual acuity
- IOP
- Dilated indirect ophthalmoscopic examination
- AE monitoring

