In order to provide standardized and well-controlled assessments of visual acuity during the study, all visual acuity assessments at a single site must be consistently done using the same lighting conditions and pin-hole during the entire study. If the same conditions and use of pin-hole cannot be used, the reason for the change in condition and pin hole should be documented.

SLIT LAMP BIOMICROSCOPY (EACH EYE):

Slit lamp biomicroscopy will be performed during the study. Observations will be graded as Normal or Abnormal. All abnormal findings, other than the endpoints being assessed by the study scales (anterior chamber cells and flare), will be documented on each patient's source document and corresponding electronic case report form (eCRF). All abnormal findings will be categorized as clinically significant (findings that may interfere with study parameters or otherwise confound the data as determined by the investigator) and not clinically significant.

The following will be examined at each visit:

- Eyelid
- Conjunctiva
- Cornea
- Iris
- Lens
- Anterior chamber

External examination and biomicroscopy will be performed using a slit lamp. Magnification will be consistent with standard clinical practice. The patient will be seated.

DURING SLIT-LAMP BIOMICROSCOPY: ANTERIOR CHAMBER CELLS AND FLARE (STUDY EYE)

The slit beam observations should be assessed in a dark room using a slit beam of 1.0 mm height and 1.0 mm width with maximum luminance, with 16x magnification, 1x1mm oblique high intensity beam fluorescein dye is to be instilled into the ocular cul-de-sac, or alternatively, fluorescein strips may be used to facilitate this examination.

Anterior Chamber Cells and Flare

The anterior chamber cell count will be recorded as the actual number of cells observed if fewer than 10 cells are seen (only white blood cells should be counted; red blood cells and pigment cells should not be counted). Flare will be graded using the SUN* Working Group grading scheme.

Anterior Chamber Cells			
Grade Number of Cells in Field			
0	0 cells		
1	1 to 10 cells		
2	11 to 20 cells		
3	21 to 50 cells		
4	> 50 cells		

Flare		
Grade Description		
0	None	
1+	Faint	
2+	Moderate iris and lens details clear	
3+	Marked iris and lens details hazy	
4+	Intense fibrin or plastic aqueous	

*Reference 3. Standardization of the Uveitis Nomenclature (SUN): Jabs et al. 2005.

INTRAOCULAR PRESSURE (IOP) PROCEDURES (EACH EYE)

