Applanation tonometry, Goldmann tonometer required. Do NOT use non-contact tonometry.

DILATED INDIRECT OPHTHALMOSCOPIC EXAMINATION (EACH EYE)

Dilated indirect ophthalmoscopic examination will be performed as indicated in the study flowchart in Appendix 2 after the patient ICF/authorization, medical history/demographics, urine pregnancy test (if applicable), pin-hole visual acuity, slit lamp biomicroscopy, and tonometry. The examination will not be performed until the patient's eyes are deemed sufficiently dilated in the opinion of the investigator. The investigator will note any findings present and whether or not the findings are clinically significant or not clinically significant. Findings which are clinically significant will be described.

The following will be examined:

- Vitreous
- Retina
- Macula
- Choroid
- Optic Nerve

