15.2 Slit-Lamp Biomicroscopy

A slit-lamp biomicroscopy examination of the cornea, conjunctiva, anterior chamber, iris, lens, and lid will be performed for both eyes at each visit. The results will be graded as normal, abnormal not clinically significant (NCS) or abnormal clinically significant (CS).

The results will be summarized using counts and percentages for each treatment group and for all patients combined at each visit for each eye (study eye and non-study eye). Percentages will be based on the number of patients in each treatment group with responses. Shift tables for the slit-lamp biomicroscopy parameters will also be provided comparing each follow-up visit to baseline (Visit 2 [Day 1]). A patient listing of the slit-lamp biomicroscopy parameters will also be produced.

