14.2.1.1	Absence of Anterior Chamber Cells at Day 15 and Ocular Pain at Day 4, Last Observation Carried Forward	Intent-to-Treat
14.2.1.2	Absence of Anterior Chamber Cells at Day 15 and Ocular Pain at Day 4, Observed Data	Intent-to-Treat
14.2.1.3	Absence of Anterior Chamber Cells at Day 15 and Ocular Pain at Day 4, Missing Data Imputed as Failures	Intent-to-Treat
14.2.1.4	Absence of Anterior Chamber Cells at Day 15 and Ocular Pain at Day 4, Observed Data	Per Protocol
14.2.2.1	Absence of Anterior Chamber Cells by Visit	Intent-to-Treat
14.2.2.2	Absence of Anterior Chamber Flare by Visit	Intent-to-Treat
14.2.2.3	Absence of Anterior Chamber Cells and Flare by Visit	Intent-to-Treat
14.2.2.4	Absence of Ocular Pain by Visit	Intent-to-Treat
14.2.3.1	Anterior Chamber Cells Grade by Visit	Intent-to-Treat
14.2.3.1	Anterior Chamber Ceas Grade by Visit Anterior Chamber Flare Grade by Visit	Intent-to-Treat
14.2.3.2	Sum of Anterior Chamber Cells and Flare Grades by Visit	Intent-to-Treat
14.2.3.4	Ocular Pain Score by Visit	Intent-to-Treat
	Summary of Treatment Emergent Adverse Events	Safety
14.3.1.1	Treatment-Emergent Adverse Events by System Organ Class	Safety
14.3.1.2		Safety
14.3.1.3	Treatment-Emergent Adverse Events by System Organ Class and	
14.3.1.4	Relationship to Study Drug	Cofoty
14.3.1.5	Serious Treatment-Emergent Adverse Events by System Organ Class	Safety
14.3.1.6	Treatment-Emergent Adverse Events Leading to Patient Discontinuation by System Organ Class	Safety
14.3.2.1.1	Slit Lamp Biomicroscopy Findings	Safety
14.3.2.1.2	Slit Lamp Biomicroscopy Findings – Shift Table	Safety
14.3.2.2.1	Dilated Indirect Ophthalmoscopic Examination Findings Safe	
14.3.2.2.2	Dilated Indirect Ophthalmoscopic Examination Findings – Shift Table	Safety

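### The slit-lamp clinical-significance grade is defined by interference with study data, so the CS column and NCS-to-CS shifts in the safety tables may not reflect importance to the patient

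*Protocol*

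**What the plan says.** "Slit lamp biomicroscopy" heads the list of safety measures in Protocol Section 6.2. Appendix 1 gives the examination method: six structures (eyelid, conjunctiva, cornea, iris, lens, anterior chamber) are each graded normal or abnormal. It adds "All abnormal findings, other than the endpoints being assessed by the study scales (anterior chamber cells and flare), will be documented", and then divides the abnormal ones into "clinically significant (findings that may interfere with study parameters or otherwise confound the data as determined by the investigator) and not clinically significant".

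SAP 15.2 carries this division into the analysis: "The results will be graded as normal, abnormal not clinically significant (NCS) or abnormal clinically significant (CS"). It gives counts by treatment group, visit and eye, and adds: "Shift tables for the slit-lamp biomicroscopy parameters will also be provided comparing each follow-up visit to baseline", baseline being Visit 2, the day after surgery. The table list in SAP Section 20 includes "Slit Lamp Biomicroscopy Findings – Shift Table" (Table 14.3.2.1.2) alongside the by-visit table (14.3.2.1.1), both in the Safety population. The SAP does not define CS or NCS.

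For dilated ophthalmoscopy, Appendix 1 asks the investigator to note "whether or not the findings are clinically significant or not clinically significant", with no definition attached. SAP 15.3 uses the same three grades.

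**The concern.** In a safety table, a reader takes CS to mean that the finding mattered for the patient. The stated rule asks something else: whether the finding may disturb the study's measurements. The two questions can have different answers, in either direction.

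This matters more here than in a well-characterised product. The Synopsis says this is the first clinical study of the suspension. The ocular effect carried forward from the nonclinical work is conjunctival irritation in rabbits, which Protocol Section 1 says "was not observed in the monkey ocular GLP toxicity study, and is readily monitorable in the clinic". The conjunctiva is one of the six slit-lamp structures, so these tables are one of the places where a reader will look for that effect. Because NCS/CS is the only gradation within abnormal, it is also the only measure of degree that they contain.

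**Working it through.** No figure in the plan depends on this point, so the check is a reading of the passages side by side, with two counts.

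**1. Which definition governs the tables.** Appendix 1 defines slit-lamp clinical significance once. Protocol Sections 6.2, 10.5 and 10.12 name or summarise the examination without defining the grade, and SAP 15.2 uses the grade undefined. The Appendix 1 wording therefore governs Tables 14.3.2.1.1 and 14.3.2.1.2.

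**2. What the definition asks.** It has two limbs, interference with study parameters and confounding of the data, both judged by the investigator. Medical importance, risk to the eye and worsening are not among them. Take four kinds of abnormal finding:

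| Finding | Medically important | May disturb an assessment | Grade under the stated rule |
|---|---|---|---|
| A | yes | yes | CS |
| B | yes | no | NCS |
| C | no | yes | CS |
| D | no | no | NCS |

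A and D get the grade that a reader would expect. B and C do not. An example of C is a harmless opacity that obscures the cell count.

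**3. What this does to the shift table.** Three grades at baseline and three at follow-up give 3 × 3 = 9 cells. Three are worsening cells: normal to NCS, normal to CS, and NCS to CS. If NCS and CS are merged, the table becomes 2 × 2 (normal or abnormal at each visit), and none of those four totals depends on the CS definition. So new abnormality and return to normal are counted correctly. Only the split within abnormal is affected. In an eye where a structure is already abnormal at Visit 2, the one worsening cell left is NCS to CS, and that cell rests wholly on the definition. Irritation in such eyes could still appear as fewer returns to normal than on placebo.

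**4. How widely the rule applies.** There are four follow-up visits (Visits 3 to 6), so 6 structures × 2 eyes × 4 visits = 48 baseline-to-follow-up comparisons per patient. With about 105 patients (35 per arm), that is at most 48 × 105 = 5,040 comparisons. This counts where the rule applies, not how often it misgrades. The documents give no rate of abnormality at Visit 2 and no rate of type B or C findings, so a misclassification rate cannot be derived.

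**5. What else captures harm.** Protocol Section 9.1 makes any unfavourable sign after the first dose an adverse event, and treats worsening of a pre-existing condition as a new one. Section 9.1.1 grades severity. Section 10.12 makes ocular treatment-emergent events in the study eye the primary safety analysis, and SAP 15.1 tabulates them by maximal severity and relationship. None of this uses the CS grade.

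**The case against.** The strongest reply is that the definition is broader than it looks. Study parameters is the title of Protocol Section 6, which covers safety as well as efficacy measures, and Appendix 2 uses the same term for its whole assessment list. A finding that alters visual acuity or intraocular pressure could be CS even if cells and pain are untouched. Irritation that causes discomfort could affect the pain score, since the pain question in Appendix 1 covers discomfort as well as pain. The grade is left to the investigator. Adverse events catch harm independently.

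Much of this stands, and it limits the point. A reader might infer that a harmful finding will be graded NCS whenever it spares the primary endpoints. The text does not support that, because the wording reaches beyond the endpoints and the investigator decides. A reader might also infer that conjunctival irritation would go undetected, or that the safety conclusion would be wrong. That does not follow either, because abnormal findings are still counted as abnormal and adverse-event reporting does not use the grade.

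The reply does not rescue the definition. The investigator's discretion is over whether a finding disturbs the study, not whether it matters to the patient. The broad reading is also circular: slit-lamp biomicroscopy is itself a listed study parameter, so any slit-lamp abnormality could be said to qualify, and the grade would then discriminate nothing. Wording that allows a narrow and a broad reading invites sites to grade differently.

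**Conclusion.** The point holds in a limited form. As worded, the slit-lamp CS grade records likely interference with the study rather than importance to the patient. The CS column and the NCS-to-CS shifts could therefore mislead a reader who uses them to judge ocular tolerability, in either direction. The defect is confined to the subdivision of abnormal in two descriptive safety tables. Normal-versus-abnormal counts, ocular adverse-event reporting and the efficacy analyses do not depend on it.

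The conclusion rests on the text alone and assumes that investigators apply Appendix 1 as written. If they grade by ordinary clinical meaning instead, the tables will be sound but the protocol will not describe what was done.

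It would go too far to say that ophthalmoscopy shares the defect. The data-interference wording is attached only to the slit-lamp grades. For ophthalmoscopy the terms are undefined, not misdefined.

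**What to change.** - In Protocol Appendix 1, replace the parenthesis with a definition of clinically significant based on the clinical importance of the finding to the patient, in the investigator's judgement.
- Repeat the definition in SAP 15.2, so that the tables carry their own meaning.
- If interference with study assessments needs to be known, record it as a separate yes/no field.
- For consistency, cite the same definition for ophthalmoscopy in Appendix 1 and SAP 15.3.

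No separate rule sending these findings to adverse-event assessment is needed, since Protocol Section 9.1 already covers new and worsened signs after the first dose.

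The cost is one sentence, a note to sites and at most one eCRF field, with no new examination. The change is best made before grading starts, because reassigning grades afterwards from the recorded descriptions would be less reliable.

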APPENDIX 2: SCHEDULE OF VISITS AND MEASUREMENTS

Study Parameter	Visit 1 (≥ -28 Days Prior to Surgery)	Visit 2 (Day 1, 24 ± 6 hrs Post- Surgery)	Visit 3 (Day 4 ²)	Visit 4 (Day 8 ²)	Visit 5 (Day 15 ³)	Visit 6 (Day 21 ² , Exit or Early Exit Visit)
Informed Consent/	Х					
HIPAA Dama ananhia Data	V					
Demographic Data	X					
Medical and Medication History	Х					
Urine Pregnancy Test (for females of childbearing potential)	Х					Х
Review of Inclusion and Exclusion Criteria	Х	Х				
Medical and Medication History Update		Х	Х	Х	Х	Х
Ocular Pain Assessment	Х	Х	Х	Х	Х	Х
Pin-hole Visual Acuity	Х	Х	Х	Х	Х	Х
Slit Lamp Biomicroscopy	Х	Х	Х	Х	Х	Х
Ocular Inflammation Assessment of Anterior Chamber Cell and Flare (at Slit-lamp Biomicroscopy)	Х	Х	X	Х	Х	Х
Intraocular Pressure Assessment	Х	Х	Х	Х	Х	Х
Randomization of Study Patients		Х				
Dilated Indirect Ophthalmoscopic Examination	Х					Х
Study Drug Instillation ¹		Х				
Study Drug and Compliance Diary Instructions and Dispensation		Х				
AE Query		Х	Х	Х	X	X
Review of Study Drug Compliance Diary			X	X	X	X
Collection of Study Drug and Compliance Diary					X	X ⁴
Exit from Study						X

¹First study drug dose will be instilled in-office at Visit 2. Patients will instill study drug twice daily athome in the morning and evening (approximately 12 hrs apart) between study visits, from Day 1 through Day 14. $^{2}\pm 1$ Day $^{3}\pm 1$ Day

⁴ In case of early termination or if patient did not return study drug prior to Visit 5.

Clinical Trial Protocol: 408-C-1307

APPENDIX 3: PROTOCOL AMENDMENTS

1. RATIONALE FOR AMENDMENT 1

The purpose of the protocol amendment is to make administrative updates throughout. Exclusion criteria #7 and #23 had additional exclusionary items specified, additional study drug dosing instructions were added to Section 7.1.2, additional details regarding escape medications were specified in Section 8.2.2, and Section 9.1.3 was deleted given Sponsor Pharmacovigilance will assess for adverse event expectedness.

2. SUMMARY OF CHANGES

In the table below the protocol text was amended by the following conventions:

- Deletions to original text are indicated by strike through letters
- Additions to amended text are indicated by **bold** letters
- Replacement of wording in the amended text are indicated by *bold and italicized* letters

Section	Reason for Amendment	Protocol Currently Reads	Amended Text
Title Page	Administrative update	[blank]	Amendment 1: 10-Feb-2014
Header	Administrative update	RTA 408 Sterile Ophthalmic Suspension	RTA 408 Sterile Ophthalmic Suspension
Header	Administrative update	Original Protocol: 21-Nov-2013	Amendment 1: 10-Feb-2014
Synopsis pg 5 – Inclusion Criteria #4	Administrative update	Have undergone unilateral cataract extraction via phacoemulsification on the day prior to study enrollment/randomization;	Have undergone unilateral cataract extraction via phacoemulsification and posterior chamber intraocular lens (PCIOL) implantation in the study eye on the day prior to study enrollment/randomization;
Synopsis pg 5 – Inclusion Criteria #5	Administrative update	Have a grade of ≥ 2 in anterior chamber cell score on day after surgery (Day 1);	Have a grade of ≥ 2 in anterior chamber cell score on day after surgery (Day 1) in the study eye;
Synopsis pg 5 – Inclusion Criteria #6	Administrative update	Have a potential post-operative pin-hole visual acuity (VA) of greater than 1.0 logarithm of the minimum angle of resolution (logMAR) in the operative eye and fellow eye as measured using an Early Treatment for Diabetic Retinopathy Study (ETDRS) chart;	Have a potential post-operative pin-hole visual acuity (VA) of greater than< 1.0 logarithm of the minimum angle of resolution (logMAR) in the operative eye and fellow eye as measured using an Early Treatment for Diabetic Retinopathy Study (ETDRS) chart;
Synopsis pg 5 – Inclusion Criteria #7	Administrative update	(For females of childbearing potential) agree to have urine pregnancy testing performed at screening (must be negative) and at exit visit ¹ ; must not be lactating; and must agree to use a medically acceptable form of birth control ² throughout the study duration.	(For females of childbearing potential) agree to have urine pregnancy testing performed at screening (must be negative) and at exit visit ¹ ; must not be lactating; and must agree to use a medically acceptable form of birth control ¹ throughout the study duration.

		¹ The subject must choose an acceptable method of birth control as specified in inclusion criterion 7 in order to continue in the study. ² Acceptable forms of birth control are spermicide with barrier, oral contraceptive, injectable or implantable method of contraception, transdermal contraceptive, intrauterine device, or surgical sterilization of partner. For non-sexually active females, abstinence will be considered an acceptable form of birth control.	¹ The subject must choose an acceptable method of birth control as specified in inclusion criterion 7 in order to continue in the study. ¹ Acceptable forms of birth control are spermicide with barrier, oral contraceptive, injectable or implantable method of contraception, transdermal contraceptive, intrauterine device, or surgical sterilization of partner. For non-sexually active females, abstinence will be considered an acceptable form of birth control.
Synopsis pg 6 – Exclusion Criteria #7	Additional exclusion criteria added	 Use the following anti-inflammatory or immunomodulating agents systemically, or in the study eye, for the duration of the study. Washout periods for medications prior to surgery are as follows: a. Systemic corticosteroids: 14 days b. Periocular injection of any corticosteroid solution: 28 days c. Corticosteroid depot in the study eye: 56 days after implantation d. Cyclosporine: 56 days e. Topical ocular corticosteroid: 7 days f. Topical ocular NSAID: 7 days 	Use anti-inflammatory agents, analgesics/pain relievers (including opioids, narcotics and other pain medications) or immunomodulating agents systemically, or in the study eye, and/or use medications for benign prostatic hyperplasia (BPH), from the washout period through for the duration of the study. Washout periods for medications prior to surgery are as follows: a. Medications for BPH (tamsulosin, silodosin, alfuzosin, finasteride): 28 days b. Systemic corticosteroids: 14 days c. Systemic analgesics/pain relievers (e.g., gabapentin, pregabalin, NSAIDs and opioids): 14 days Note: Use of acetaminophen (up to 4,000 mg/day) and 'baby' aspirin (up to 81 mg/day) during the study are allowed. Use of an opioid during cataract surgery is allowed. d. Periocular injection of any corticosteroid solution: 28 days

			 e. Corticosteroid depot in the study eye: 56 days after implantation f. Cyclosporine: 56 days g. Topical ocular corticosteroid: 7 days h. Topical ocular NSAID: 7 days
Synopsis pg 7 – Exclusion Criteria #9	Administrative update	Have an IOP ≤ 5 mmHg in either eye;	Have an intraocular pressure (IOP) \leq 5 mmHg in either eye;
Synopsis pg 7 – Exclusion Criteria #16	Administrative update	Have had corneal or retinal surgery (laser or incisional) within the past 6 months, or be planning to have laser or incisional surgery during the study period in the study eye;	Have had corneal or retinal surgery (laser or incisional) within the past 6 months, or be planning to have laser or incisional surgery during the study period in the study eye (other than cataract surgery);
Synopsis pg 7 – Exclusion Criteria #17	Administrative update	Have a scheduled surgery in the contralateral eye during the study;	Have a surgery planned or scheduled surgery in for the contralateral eye during the study;
Synopsis Pg 8 – Exclusion Criteria #23	Additional exclusion criteria added	Have undergone a vitrectomy procedure in addition to the cataract extraction procedure in the study eye;	Have undergone any other ophthalmic surgical procedure (e.g., vitrectomy, relaxing incisions, iridectomy, conjunctival excisions, use of iris hooks or other iris dilators, etc.) a vitrectomy- procedure in addition to the cataract extraction procedure and PCIOL implantation in the study eye;
Synopsis Pg 8 – Exclusion Criteria #24	Administrative update	Have previously enrolled in this clinical study, or will be participating during the follow-up period in another clinical trial that could confound the treatment or outcomes of this investigation;	Have previously enrolled in this clinical study, or will beare planning to participate in another clinical trial during the follow-up period, in another clinical trial that could confound the treatment or outcomes of this investigation;
Synopsis Pg 10 – General Statistical	Administrative update	If in addition to a statistically significant test of the difference in the proportion of study eyes with	If in addition to a statistically significant test of the difference in the proportion of study eyes with

		-	
Methods and Types of Analyses: Efficacy Analysis (5th Paragraph)		absence of anterior chamber cells at Visit 5 (Day 15) in favor of RTA 408 Ophthalmic Suspension, the test of the difference in the proportion of study eyes with absence of ocular pain at Visit 3 (Day 4) is statistically significant in favor of RTA 408 Ophthalmic Suspension, then RTA 408 Ophthalmic Suspension will be declared to be superior to placebo in both the proportion of study eyes with absence of anterior chamber cells at Visit 5 (Day 15) and the proportion of study eyes with absence of ocular pain at Visit 3 (Day 4).	absence of anterior chamber cells at Visit 5 (Day- 15) in favor of RTA 408 Ophthalmic Suspension, the test of the difference in the proportion of study eyes with absence of ocular pain at Visit 3- (Day 4) is statistically significant in favor of RTA 408 Ophthalmic Suspension, then RTA 408- Ophthalmic Suspension will be declared to be superior to placebo in both the proportion of study eyes with absence of anterior chamber cells at Visit 5 (Day 15) and the proportion of study- eyes with absence of ocular pain at Visit 3 (Day- 4).
Synopsis Pg 11 – General Statistical Methods and Types of Analyses: General Considerations (5 th and 6 th Paragraphs)	Administrative update	The secondary efficacy variables, study eyes with absence of anterior chamber cells (Visits 3, 4 or 6), study eyes with absence of pain (Visits 4, 5 or 6) and study eyes with absence of flare (Visits 3, 4, 5 or 6) will be summarized and analyzed similarly to the primary efficacy summaries and analyses. Additionally, anterior chamber cells and flare as well as pain at each visit and change from baseline will be summarized using continuous and discrete summary statistics. The sum of anterior chamber cells and flare grade will be summarized and analyzed similarly to anterior chamber cells and flare separately.	The secondary efficacy variables, study eyes with absence of anterior chamber cells (Visits 3, 4 or 6), study eyes with absence of pain (Visits 4, 5 or 6) and study eyes with absence of flare (Visits 3, 4, 5 or 6) will be summarized and analyzed similarly to the primary efficacy summaries and analyses . Additionally, anterior chamber cells and flare as well as pain at each visit and change from baseline will be summarized using continuous and discrete summary statistics. The sum of anterior chamber cells and flare grade will be summarized and analyzed similarly to anterior chamber cells and flare separately.
List of Abbreviations	Administrative update	 PID Pic in die (twice daily)	 PID Pis in dia (twice doily)
		CER Code of Federal Regulations	BPH Benjan prostatic hyperplasia
			CFR Code of Federal Regulations

		NSAID Non-steroidal anti-inflammatory agent	
		PDR Proliferative diabetic retinopathy	NSAID Non-steroidal anti-inflammatory agent
			PCIOL Posterior chamber intraocular lens
			PDR Proliferative diabetic retinopathy
Section 4 Paragraph 2	Administrative update	The Investigator will then perform a slit lamp biomicroscopic examination with IOP measurement, and grading of anterior chamber inflammation. A dilated indirect ophthalmoscopic examination will also be performed. Female patients of childbearing potential will be given a urine pregnancy test.	The Investigator will then perform a slit lamp biomicroscopic examination with intraocular pressure (IOP) measurement, and grading of anterior chamber inflammation. A dilated indirect ophthalmoscopic examination will also be performed. Female patients of childbearing potential will be given a urine pregnancy test.
Section 4 Paragraph 3	Administrative update	Qualifying patients (with ≥ 2 score in anterior chamber cell, IOP ≤ 22 mm Hg) will then be randomized to one of the following treatment groups (in a 1:1:1 ratio): RTA 408 Ophthalmic Suspension 0.5% (N=35), RTA 408 Ophthalmic Suspension 1.0% (N=35), or placebo for RTA 408 Ophthalmic Suspension (N=35).	Qualifying patients (with ≥ 2 score in anterior- chamber cell, IOP ≤ 22 mm Hg)-will then be randomized to one of the following treatment groups (in a 1:1:1 ratio): RTA 408 Ophthalmic Suspension 0.5% (N=35), RTA 408 Ophthalmic Suspension 1.0% (N=35), or placebo for RTA 408 Ophthalmic Suspension (N=35).
Section 5.3 Inclusion Criteria #4	Administrative update	Have undergone unilateral cataract extraction via phacoemulsification on the day prior to study enrollment/randomization;	Have undergone unilateral cataract extraction via phacoemulsification and posterior chamber intraocular lens (PCIOL) implantation in the study eye on the day prior to study enrollment/randomization;
Section 5.3 Inclusion Criteria #5	Administrative update	Have a grade of ≥ 2 in anterior chamber cell score on day after surgery (Day 1);	Have a grade of ≥ 2 in anterior chamber cell score on day after surgery (Day 1) in the study eye;
Section 5.3	Administrative	Have a potential post-operative pin-hole visual	Have a potential post-operative pin-hole visual

Inclusion Criteria #6	update	acuity (VA) of greater than 1.0 logarithm of the minimum angle of resolution (logMAR) in the operative eye and fellow eye as measured using an Early Treatment for Diabetic Retinopathy Study (ETDRS) chart;	acuity (VA) of greater than< 1.0 logarithm of the minimum angle of resolution (logMAR) in the operative eye and fellow eye as measured using an Early Treatment for Diabetic Retinopathy Study (ETDRS) chart;
Section 5.3 Inclusion Criteria #7	Administrative update	(For females of childbearing potential) agree to have urine pregnancy testing performed at screening (must be negative) and at exit visit ¹ ; must not be lactating; and must agree to use a medically acceptable form of birth control ² throughout the study duration.	(For females of childbearing potential) agree to have urine pregnancy testing performed at screening (must be negative) and at exit visit [‡] ; must not be lactating; and must agree to use a medically acceptable form of birth control ¹ throughout the study duration.
		¹ The subject must choose an acceptable method of birth control as specified in inclusion criterion 7 in order to continue in the study. ² Acceptable forms of birth control are spermicide with barrier, oral contraceptive, injectable or implantable method of contraception, transdermal contraceptive, intrauterine device, or surgical sterilization of partner. For non-sexually active females, abstinence will be considered an acceptable form of birth control.	 ¹ The subject must choose an acceptable method- of birth control as specified in inclusion criterion. 7 in order to continue in the study. ¹ Acceptable forms of birth control are spermicide with barrier, oral contraceptive, injectable or implantable method of contraception, transdermal contraceptive, intrauterine device, or surgical sterilization of partner. For non-sexually active females, abstinence will be considered an acceptable form of birth control.
Section 5.4 Exclusion Criteria #7	Additional exclusion criteria added	Use the following anti-inflammatory or immunomodulating agents systemically, or in the study eye, for the duration of the study. Washout periods for medications prior to surgery are as follows: a. Systemic corticosteroids: 14 days b. Periocular injection of any corticosteroid solution: 28 days	Use anti-inflammatory agents , analgesics/pain relievers (including opioids, narcotics and other pain medications) or immunomodulating agents systemically, or in the study eye, and/or use medications for benign prostatic hyperplasia (BPH), from the washout period through for the duration of the study. Washout periods for medications prior to surgery are as

		 c. Corticosteroid depot in the study eye: 56 days after implantation d. Cyclosporine: 56 days e. Topical ocular corticosteroid: 7 days f. Topical ocular NSAID: 7 days 	 follows: a. Medications for BPH (tamsulosin, silodosin, alfuzosin, finasteride): 28 days b. Systemic corticosteroids: 14 days c. Systemic analgesics/pain relievers (e.g., gabapentin, pregabalin, NSAIDs and opioids): 14 days Note: Use of acetaminophen (up to 4,000 mg/day) and 'baby' aspirin (up to 81 mg/day) during the study are allowed. Use of an opioid during cataract surgery is allowed. d. Periocular injection of any corticosteroid solution: 28 days e. Corticosteroid depot in the study eye: 56 days after implantation f. Cyclosporine: 56 days g. Topical ocular NSAID: 7 days
Section 5.4 Exclusion Criteria #9	Administrative update	Have an IOP ≤ 5 mmHg in either eye;	Have an intraocular pressure (IOP) \leq 5 mmHg in either eye;
Section 5.4 Exclusion Criteria #16	Administrative update	Have had corneal or retinal surgery (laser or incisional) within the past 6 months, or be planning to have laser or incisional surgery during the study period in the study eye;	Have had corneal or retinal surgery (laser or incisional) within the past 6 months, or be planning to have laser or incisional surgery during the study period in the study eye (other than cataract surgery);
Section 5.4 Exclusion Criteria #17	Administrative update	Have a scheduled surgery in the contralateral eye during the study;	Have a surgery planned or scheduled surgery in for the contralateral eye during the study;

Section 5.4 Exclusion Criteria #23	Additional exclusion criteria added	Have undergone a vitrectomy procedure in addition to the cataract extraction procedure in the study eye;	Have undergone any other ophthalmic surgical procedure (e.g., vitrectomy, relaxing incisions, iridectomy, conjunctival excisions, use of iris hooks or other iris dilators, etc.) a vitrectomy procedure in addition to the cataract extraction procedure and PCIOL implantation in the study eye;
Section 5.4 Exclusion Criteria #24	Administrative update	Have previously enrolled in this clinical study, or will be participating during the follow-up period in another clinical trial that could confound the treatment or outcomes of this investigation;	Have previously enrolled in this clinical study, or will beare planning to participate in another clinical trial participating during the follow-up period, in another clinical trial that could confound the treatment or outcomes of this investigation;
Section 6.1.2	Administrative update	This clinical study is designed to evaluate the efficacy and safety of two concentrations of RTA 408 Ophthalmic Suspension compared to placebo in the treatment of inflammation and pain following ocular surgery. To demonstrate clinical efficacy, RTA 408 Ophthalmic Suspension must be effective in eliminating anterior chamber cells (i.e. score of '0') at Visit 5 (Day 15) post-ocular surgery. If, in addition to absence of anterior chamber cells, RTA 408 Ophthalmic Suspension is also effective in elimination of ocular pain (i.e. score of '0') at Visit 3 (Day 4) post-ocular surgery, then absence of pain will also be claimed.	This clinical study is designed to evaluate the efficacy and safety of two concentrations of RTA 408 Ophthalmic Suspension compared to placebo- in the treatment of inflammation and pain- following ocular surgery. To demonstrate clinical- efficacy, RTA 408 Ophthalmic Suspension must- be effective in eliminating anterior chamber cells (i.e. score of '0') at Visit 5 (Day 15) post ocular- surgery. If, in addition to absence of anterior- chamber cells, RTA 408 Ophthalmic Suspension- is also effective in elimination of ocular pain (i.e. score of '0') at Visit 3 (Day 4) post ocular- surgery, then absence of pain will also be- claimed.
Section 7.1.2 3rd Bullet Point	Additional dosing instructions specified	Instructions to patients on study drug administration will include: Remove from refrigerator. SHAKE WELL BEFORE USE. Instill one drop twice daily for 14 days in the	Instructions to patients on study drug administration will include: Remove from refrigerator. SHAKE WELL BEFORE USE. Instill one drop twice daily for 14 days in

		morning and evening (approximately 12 hours apart) in the eye that underwent surgery. Return drug to refrigerator for storage after each use. Discontinue use of the study drug after completing second dose on Day 14. Keep out of reach of children.	the morning and evening (approximately 12 hours apart) in the eye that underwent surgery. Study drug must be not be instilled within 30 minutes of after instillation of any other ocular medications or artificial tears. Return the study drug to refrigerator for storage after each use. Discontinue use of the study drug after instilling completing the second dose on Day 14. Keep out of reach of children.
